9.7. Neutralizing antibodies and 765IGF-MTX Toxicity/Response

Serum samples from before the infusion on D1 of cycle 1 and before the infusion on D1 and D15 of cycle 2, and on D15 of cycles 4 and 6 will be analyzed for the presence of neutralizing antibodies. In this assay, serum will be mixed with 765IGF-MTX in an in vitro assay for killing of human MCF7 breast cancer cells to determine whether the addition of patient serum affects the minimum inhibitory concentration of 765IGF-MTX in inhibiting

growth of MCF7 cells. Please see the laboratory manual for biomarker collection procedures.

A descriptive analysis will be done correlating neutralizing antibody presence or levels with clinical response to, and toxicity of, 765IGF-MTX.

9.8. IGF-1R expression level in diseased cells of bone marrow aspirate via IHC and flow cytometry

When bone marrow aspirates are collected from patients, a portion will be clotted, fixed, and paraffin embedded; and a second portion will be shipped fresh the same day to Charles River Laboratories (Reno, NV) for flow cytometry assay of IGF-1R and CD34. A pathology report will be prepared for the fixed sample. The fixed samples will be held at Mayo Clinic and shipped together at the end of the study with their pathology reports to Quest Diagnostics for IGF-1R expression level testing by IHC with their test code 19429X.

The fresh second portion of the bone marrow aspirate will be kept at room temperature and shipped on the day of collection in an insulated container at room temperature to Charles River, Inc. (Reno, NV), for testing of IGF-1R and CD34 expression by flow cytometry. This assay will be similar to that of He et al.²⁸

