7.2. Dose Modifications

7.2.1. Start of a New Cycle

Toxicity and adverse will be classified according to NCI's Common Terminology Criteria for Adverse Events Version 4.0 (CTCAE). A copy of the CTCAE can be downloaded from the CTEP home page:

(http://ctep.cancer.gov/protocolDevelopment/electronic_applications/ctc.htm#ctc_40).

Assessment of clinical benefit will be performed by investigators at the end of cycle 1 and confirmed with bone marrow studies as per MDS, CMML or O-AML specific response criteria (Appendices I and II) done at the end of cycles #2, 4, and 6 (i.e., at 8, 16, and 24 weeks, each +/- 7 days) and at the discretion of the physician thereafter.

A new treatment cycle will only be initiated when all of the following conditions are met:

- non- hematologic treatment related toxicities have improved to \leq Grade 1 (CTCAE v.4.0) or to the patient's baseline values (except alopecia)
- Platelets per 7.1 (platelets $> 10 \times 10^9/L$)

If blood counts are below this threshold at the 4 week point, blood work is to be repeated weekly until counts are at an acceptable level. Treatment will be restarted with appropriate dose modifications provided CTCAE hematologic grade ≥ 4 is not prolonged for more than 6 weeks in the absence of persistent disease. If treatment is unable to restart within 4 weeks of the planned treatment date, the patient will be permanently discontinued from study therapy.

CTCAE v.4.0 Adverse Effects Terms & Descriptions (see below for allergic reaction/hypersensitivity)	765IGF-MTX Dose Modifications (for treatment-related toxicities deemed clinically significant)
Any persistent (>4 weeks) grade 2 treatment-related non-hematologic toxicity	Drop to next lower dose level or discontinue treatment.
Grade 4 or greater treatment-related hematological toxicity for >7 days.	Drop to next lower dose level or discontinue treatment.
Grade 3 or greater treatment-related clinical non-hematological toxicity, excluding grade 3 nausea, vomiting, or diarrhea without maximal medical intervention and/or prophylaxis.	Drop to next lower dose level or discontinue treatment.
Febrile neutropenia.	Drop to next lower dose level or discontinue treatment.
Platelets less than $10 \times 10^9/L$	Wait to improve and then drop to next lower dose level or discontinue treatment.

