8.1. Standard of Care Procedures

	Baseline, within 28 days of enrollment	Each treatment cycle ^a			Every 8 weeks (± 1 week)	30 days (± 1 week) after final dose of 765IGF-MTX ¹
		Day 1 ² (±1 day)	Day 8 (±1 day)	Day 15 (±1 day)		
Signed consent (Registration/ Enrollment must occur within 30 days.)	X					
Medical history	X	X				X
Review of prior therapy	X					
Bone marrow biopsy and aspirate confirming disease and blast count ³	X				X ³	
Physical exam	X	X				X
Vital signs	X	X	X	X		X
Height, weight	X	X				X
Concomitant meds review	X	X	X	X		X
Performance status	X	X				X
Symptom and toxicity	X	X	X	X		X ³
CBC w/ diff	X	X	X	X		X
CMP (with: calcium, glucose, sodium, potassium, CO ₂ , chloride, BUN, creatinine, albumin, ALT, AST, bilirubin, alkaline phosphatase, total protein)	X	X	X	X		X
Uric acid (cycle 1 only)	X	X		X		
LDH	X	X				
HbA1C for diabetic patients	X					X
Serum pregnancy test for females of child- bearing potential	X					
ECG ⁴	X	X				X
765IGF-MTX administration			X	X		

^a Subsequent cycles beyond cycle 1 must meet the criteria found in section 7.3 and may begin 1 day earlier or up to 2 days later to accommodate scheduling issues.

¹ For patients who leave treatment with a response, repeat appropriate disease assessment every 6-12 weeks until progression or start of a new treatment.

² For cycle 1 only, tests and procedures do not need to be repeated if done within 3 days of day 1.

³ Bone marrow biopsy should be at end of end of cycle 2, and every 2 cycles thereafter to cycle 6. Patients who achieve response (CR) could have repeat bone marrow biopsies per MD discretion.

⁴ ECG performed at screening, at cycle 1 and at the end of study visit 30 days after the final dose.

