8.2. Research Related Procedures

	Baseline (within 28 days of Cycle 1, D1)	C1D1	C1 D15	C2 D1	C2 D15	Every 8 weeks (± 1 week) up to week 24	Cycles 4 and 6, D15
PKs per section 9.1		x ¹	x ¹				
ECG (QT study) done during PK blood collection per section 9.3. PK patients only. ²		x ²	x ²				
Serum IGF-1 level. All subjects.		x ³		x ³	x ³		
Plasma and whole blood IGF-1R level. All subjects.		x ³		x ³	x ³		x ³
Anti-765IGF antibody assay. All subjects.		x ³		x ³	x ³		x ³
Neutralizing antibodies. All subjects.		x ³		x ³	x ³		x ³
IGF-1R expression in bone marrow biopsy and aspirate by IHC and flow cytometry. All subjects.	x ⁴					x ⁴	
IGF-1R expression in blood cells by flow cytometry. All subjects.	x ⁵					x ⁵	

¹ Done only in the PK patients in the MTD. Pre-765IGF-MTX infusion (at the time of am labs if am labs are within one hour of 765IGF-MTX infusion), 5 min before the infusion ends (+/- 5 minutes), and at the following time points after completion of the infusion: 30 min (+/- 5 minutes), 60 min (+/- 15 minutes), 2 h (+/- 15 minutes), 4 h (+/- 15 minutes), 6 h (+/- 15 minutes), 8 h (+/- 15 minutes and 24 h (+/- 2 hours)). The 8 hour time point will be collected on day 1 but not on day 15.

² Done only in PK patients in the MTD. Pre-765IGF-MTX infusion (+/- 5 minutes), and 30 min (+/- 5 minutes) after starting the infusion, at the following time points after completion of the infusion: 60 min (+/- 15 minutes) and 3 hours (+/- 15 minutes). In all patients, ECG is done at baseline, on day 1, cycle 1 (before the infusion), and 30 days (± 1 week) after the final dose (see section 8.1).

³ Blood draw prior to infusion

⁴ Bone marrow biopsy and aspirate will be collected at baseline and every 8 weeks (± 1 week) up to week 24, i.e., after cycles 2, 4, and 6, before the first dose of the next cycle. If no bone marrow aspirate viably frozen for flow cytometry is available from a patient in the 28-day baseline period before cycle 1, day 1, the patient may still enroll and no new bone marrow biopsy will be required for a baseline sample.

⁵ Whole blood collection in EDTA tubes.

9. Correlative Studies

Information on the collection of blood samples for the correlative studies (collection tubes to be used, volume of blood drawn, collection processing, aliquot procedure and storage, and particular assay to be used) can be found in a laboratory manual to be supplied.

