9.5. Plasma and whole blood IGF-1R Level and 765IGF-MTX Toxicity/Response

Plasma and whole blood samples from before the infusion on D1 of cycle 1, and before the infusion on D1 and D15 of cycle 2 and on D15 of cycles 4 and 6 will be collected from each patient to determine if pre- and within-treatment serum and blood IGF-1R level is associated with 765IGF-MTX toxicity and/or response. Quantification of IGF-1R in plasma will be performed by IGF Oncology using western blotting. A descriptive analysis will be done between clinical response and marker levels. Please see the laboratory manual for biomarker collection procedures.

9.6. Formation of anti-765IGF-MTX antibodies.

Serum samples from before the infusion on D1 of cycle 1, and before the infusion on D1 and D15 of cycle 2 will be collected from each patient and analyzed for anti-drug antibodies by an assay the sponsor has used for detecting anti-765IGF-MTX antibodies in preclinical tests in dogs and rats. The assay is a sandwich ELISA involving plating serum in 96-well plates, adding drug to the wells of the plates to bind to any anti-drug antibodies that may be present in the serum, and then detecting bound 765IGF-MTX drug with an anti-IGF-HRP conjugate antibody from R&D Systems, Quantikine human IGF-1 ELISA kit.

That sandwich assay detects antibodies against 765IGF-MTX.

The serum samples will also be analyzed for the presence of neutralizing antibodies. In this assay, serum will be mixed with 765IGF-MTX in an in vitro assay for killing of human MCF7 breast cancer cells to determine whether the addition of patient serum affects the minimum inhibitory concentration of 765IGF-MTX in inhibiting growth of MCF7 cells. This assay will be performed on the same serum samples collected before treatment on Cycle 2, days 1 and 15 and on day 15 of cycles 4 and 6. Please see the laboratory manual for biomarker collection procedures.

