13.5.6 Antibody formation against 765IGF-MTX: Serum samples from before infusion on D1 of cycle 1, and before infusion on D1 and D15 of cycle 2 and day 15 of cycles 4 and 6 will be collected and analyzed for anti-765IGF-MTX antibodies. A descriptive analysis will be done correlating anti-765IGF-MTX antibody presence or levels with clinical response and toxicity.

13.5.7 Neutralizing antibodies and 765IGF-MTX toxicity/response: Serum samples from before infusion on D1 of cycle 1 and before infusion on D1 and D15 of cycle 2 and D15 of cycles 4 and 6 will be collected for presence of neutralizing antibodies. A descriptive analysis will be done correlating presence or levels of neutralizing antibodies with clinical response and toxicity.

13.5.8 IGF-1R expression level in bone marrow biopsies via IHC and flow cytometry and IGF-1R expression level in blood cells by flow cytometry: IGF-1R expression at baseline will be performed on paraffin-embedded fixed bone marrow aspirates by Quest Diagnostics by IHC and IGF-1R expression at baseline will be performed on fresh viable bone marrow aspirates and fresh whole blood by Charles River, Inc. by flow cytometry. If sample sizes are small and heterogeneous, clinical responses will be reported by dose and disease (MDS, CMML, or O-AML) type

14 Conduct of the Study

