Appendix I – Response Criteria for Acute Leukemia

Acute Myeloid Leukemia⁴⁵

Table 5. Response criteria in AML

Category	Definition
Complete remission (CR)*	Bone marrow blasts < 5%; absence of blasts with Auer rods; absence of extramedullary disease; absolute neutrophil count $> 1.0 \times 10^9/L$ (1000/ μ L); platelet count $> 100 \times 10^9/L$ (100 000/ μ L); independence of red cell transfusions
CR with incomplete recovery (CRI)†	All CR criteria except for residual neutropenia ($< 1.0 \times 10^9/L$ [1000/ μ L]) or thrombocytopenia ($< 100 \times 10^9/L$ [100 000/ μ L])
Morphologic leukemia-free state‡	Bone marrow blasts < 5%; absence of blasts with Auer rods; absence of extramedullary disease; no hematologic recovery required
Partial remission (PR)	Relevant in the setting of phase 1 and 2 clinical trials only; all hematologic criteria of CR; decrease of bone marrow blast percentage to 5% to 25%; and decrease of pretreatment bone marrow blast percentage by at least 50%
Cytogenetic CR (CRC)§	Reversion to a normal karyotype at the time of morphologic CR (or CRI) in cases with an abnormal karyotype at the time of diagnosis; based on the evaluation of 20 metaphase cells from bone marrow
Molecular CR (CRM)¶	No standard definition; depends on molecular target
Treatment failure	
Resistant disease (RD)	Failure to achieve CR or CRI (general practice; phase 2/3 trials), or failure to achieve CR, CRI, or PR (phase 1 trials); only includes patients surviving ≥ 7 days following completion of initial treatment, with evidence of persistent leukemia by blood and/or bone marrow examination
Death in aplasia	Deaths occurring ≥ 7 days following completion of initial treatment while cytopenic; with an aplastic or hypoplastic bone marrow obtained within 7 days of death, without evidence of persistent leukemia
Death from indeterminate cause	Deaths occurring before completion of therapy, or < 7 days following its completion; or deaths occurring ≥ 7 days following completion of initial therapy with no blasts in the blood, but no bone marrow examination available
Relapse	Bone marrow blasts $\geq 5\%$; or reappearance of blasts in the blood; or development of extramedullary disease

Table 6. Outcome measures in AML

Category	Definition
Overall survival	Defined for all patients of a trial; measured from the date of entry into a study to the date of death from any cause; patients not known to have died at last follow-up are censored on the date they were last known to be alive

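### Section 9.8 sends fixed marrow samples to the IHC laboratory with their pathology reports and without coding, so outcome-related findings could reach the person scoring IGF-1R (minor).

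*Combined protocol and SAP*

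**What the plan says.** Section 9.8 divides each marrow aspirate. One portion is fixed and embedded, and for it "A pathology report will be prepared for the fixed sample". The fixed samples stay at the clinical site and are then "shipped together at the end of the study with their pathology reports to Quest Diagnostics for IGF-1R expression level testing by IHC". The other portion goes fresh to a different laboratory on the day of collection for flow cytometry, and no report is said to go with it.

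The schedule in Section 8.2 lists marrow for IGF-1R by IHC and flow cytometry at baseline and every 8 weeks up to week 24, "i.e., after cycles 2, 4, and 6, before the first dose of the next cycle". Section 13.5.8 is narrower: "IGF-1R expression at baseline will be performed on paraffin-embedded fixed bone marrow aspirates by Quest Diagnostics by IHC".

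The same marrow examinations serve the clinical assessment. Section 8.1 lists "Bone marrow biopsy and aspirate confirming disease and blast count", and Section 7.2.1 has clinical benefit "confirmed with bone marrow studies as per MDS, CMML or O-AML specific response criteria". In Appendix I, CR in AML begins with "Bone marrow blasts < 5%; absence of blasts with Auer rods"; the MDS criteria in Appendix II also use the marrow blast percentage.

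For the blood marker, Section 9.5 says: "Quantification of IGF-1R in plasma will be performed by IGF Oncology using western blotting".

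**The concern.** A marker meant to be set beside clinical response should be scored by someone who does not know the response. Here the plan prescribes the opposite arrangement: the reports travel with the samples, in one shipment, once the study is over and outcomes are known. If post-treatment reports are in that shipment, a reader could tell which marrows had cleared their blasts.

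The direction a reader might expect is clear from the Study Rationale (Section 1.3), which rests on overexpression of IGF-1R in malignant cells and uptake of the drug through that receptor. Cohorts are 1 to 9 patients per dose level, so a few shifted scores could create or blur a pattern between tissue IGF-1R and response. A score read with the outcome in view cannot be corrected afterwards, so any change has to be made before the shipment.

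**Working it through.** This is mainly a comparison of sections; the plan has no figure of its own to reproduce.

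1. **What travels.** Section 9.8 prepares a pathology report for the fixed sample and ships samples and reports together at study end.

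2. **What the reports are likely to contain.** Their content is not specified. Section 8.1 uses the marrow to confirm disease and count blasts, so blast findings are a reasonable inference. A formal statement of remission may be absent.

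3. **How close that is to the outcome.** Section 7.2.1 confirms response on the marrows at the end of cycles 2, 4 and 6, which are the marrows that Section 8.2 lists for IGF-1R. Appendices I and II use marrow blasts for CR, CRi or marrow CR, and PR. CR and PR also need peripheral blood criteria, and the MDS responses must last at least 4 weeks. A marrow report is therefore part of the response call and not the whole of it.

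4. **Whether anything masks the scorer.** Sections 3.3, 8.1, 8.2, 9.4 to 9.9 and 13.2 to 13.5 contain no coding, redaction, limit on who sees the reports, IHC scoring rule, or locking of scores before linkage. The laboratory manual is introduced at the start of Section 9 for blood samples, and Section 9.8 does not refer to it.

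5. **Which marrows are stained.** Section 8.2 has baseline and after cycles 2, 4 and 6; Section 13.5.8 has baseline only. Under 8.2, post-treatment marrows are scored with their own reports at hand. Under 13.5.8 none is scored, and post-treatment findings reach the scorer only if later reports are in the same shipment.

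6. **Which analysis is exposed.** Section 13.5.8 reports clinical responses under the tissue IGF-1R heading but names no test of association. The two-sample t-test and Wilcoxon test are in Section 13.5.2, for pharmacodynamic parameters. Endpoint 3.3.3 defines the IGF-1R measure there as plasma and whole blood, while tissue expression is a separate endpoint (3.3.8).

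7. **Whether the bias can be sized.** It cannot. Section 13.1 leaves the sample size open, and no response rate, score distribution or reader variability is given. The following only shows how far an answer depends on assumptions. Suppose there is no true difference, scoring shifts responders by d standard deviations, and a two-sided 5% t-test is applied to n1 responders and n2 non-responders. The noncentrality is d × √(n1·n2/(n1+n2)). With 20 patients (assumed) there are 18 degrees of freedom and the critical value is 2.101. At d = 0.5 (assumed):

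| Responders vs non-responders | Noncentrality | Chance of a positive test |
|---|---|---|
| 5 vs 15 | 0.968 | 15% |
| 3 vs 17 | 0.798 | 12% |
| 2 vs 18 | 0.671 | 10% |
| 1 vs 19 | 0.487 | 7.5% |

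For 5 vs 15, d = 0.25 gives 7% and d = 0.75 gives 28%. None of these inputs comes from the documents, and the test is not planned for IHC.

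**The case against.** The strongest reply is that the text says only that reports travel with samples. It does not say that the scorer opens them, that they show dates, or that they state remission. This stands, and the point is limited to exposure that the plan leaves open.

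A reader might infer that the plan hands the scorer the outcome, and that false associations would be common: 15% at the 5 vs 15 split, or 44% for a before/after comparison in 15 patients shifted by 0.5 SD of the within-patient change. The documents do not support this. No paired test of IHC is planned, the t-test belongs to the blood markers, and the shifts and group sizes are assumed.

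A reader might also extend the concern to the sponsor's plasma western blots. A formal test against response is planned there, and the sponsor does the assay. But Section 9.5 refers collection procedures to a laboratory manual that is not among the documents, so whether those samples are coded cannot be judged.

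It can also be said that masking is incomplete: the assay concerns diseased cells, and a reader sees blasts on the slide. That is true, but the slide alone does not show the patient, the cycle or the reported blast percentage. Finally, flow cytometry on the fresh portion gives a second tissue measure that is not described as shipped with a report. That lowers the stakes without closing the gap.

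**Conclusion.** The point holds as a minor one. Section 9.8 sets out a procedure that could put outcome-related information before the person measuring endpoint 3.3.8, and nothing in the documents prevents it. The conclusion rests on one inference, that the marrow reports carry blast findings, and on the possibility, not stated in the text, that the scorer sees them.

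The size of any bias is unknown and cannot be derived from the plan. It would touch only the IHC levels and their description beside response. The response calls and the safety and MTD conclusions do not depend on it. The disagreement between Sections 8.2 and 13.5.8 determines how direct the exposure is and needs settling in any case.

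**What to change.** - **Section 9.8, shipment.** Ship coded samples in random order without the pathology reports, with a sheet giving only specimen type and adequacy. If the laboratory needs a report, redact the date, cycle, blast percentage and disease-status lines.
- **Section 9.8, scoring.** Lock the IHC scores before they are linked to response. Release any further pathology detail only after that lock.
- **Sections 8.2 and 13.5.8.** State in both which marrows are stained by IHC: baseline only, or baseline and after cycles 2, 4 and 6.
- **Section 9.5 (secondary).** Send coded plasma aliquots, without time point or outcome, for the sponsor's western blots, unless the laboratory manual already provides for this.

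The cost is a little clerical work, since the fixed samples are already held and shipped in one batch. Nothing changes for patients, visits or sample collection. The downside is that the IHC laboratory scores without clinical context.

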9.9. IGF-1R expression level in diseased cells of whole blood via flow cytometry

Whole blood will be collected in EDTA tubes (6 ml) and shipped overnight the same day in an insulated container at room temperature to Charles River, Inc., for testing of IGF-1R and CD34 expression by flow cytometry. This assay will be similar to that of He et al.²⁸ This collection and testing will be at baseline and every 8 weeks after treatment is begun.

10. Drug Formulation and Procurement

10.1. 765IGF-MTX

10.1.1. Other names

765IGF-methotrexate, IGF-methotrexate, IGF-methotrexate conjugate, IGF-MTX

10.1.2. Classification

Insulin-Like Growth Factor and an enzyme inhibitor of dihydrofolic acid reductase (methotrexate)

10.1.3. How supplied

765IGF-MTX is supplied as a 5 ml sterile solution at 4.0 μ eq per ml 765IGF-MTX concentration in aqueous 10 mM HCl in a 10 ml glass vial.

10.1.4. Availability

765IGF-MTX will be provided by IGF Oncology with approval of the FDA for investigational purposes. (IND # 116840).

10.1.5. Description

765IGF-MTX is formulated as a sterile solution at 4.0 μ eq/ml (4.0 μ mol methotrexate groups per ml) in 10 mM HCl in a 10 ml vial. The appropriate volume of the drug is then added to 250 ml of either 5% or 10% dextrose (per discretion of Principal Investigator) on the day of administration.

10.1.6. Storage, Handling, and Accountability

The final product of 765IGF-MTX is stored refrigerated at 4°C. Studies at elevated temperatures suggest the drug is stable for at least 2 years when stored in this manner.

